## RANDOM ASSIGNMENT TO STUDY CONDITIONS

### Overview

The [random assignment process](#) is the collective responsibility of student investigators and the outreach coordinator. The separate roles of these staff members in this process are described in separate sections below. The day of random assignment must occur within two weeks of the first meeting. If a participant has not completed the necessary procedures for randomization by the two-week time point, then that participant should be permanently discharged from the study.

### Procedures

**Overview.** All staff will be prepared for the intake assessment. After the informed consent is signed by the participant, the Outreach Coordinator notifies the WMU staff and brings the participant to the computer terminal. Student investigators will have the primary responsibility for randomly assigning participants to one of the two study conditions. After completing the randomization procedure, the Outreach Coordinator and WMU staff should train participants how to use the SteadyRx app and PillWatch function (if in SteadyRx group), distribute CTPayer card, and update relevant data logs.

**Randomization Variables.** The proposed pilot study will feature a 2 group, randomized controlled, parallel group design. In order to assess the effectiveness of the proposed intervention as a whole, participants will be assigned to receive usual care (Control Group) or the SteadyRx smartphone intervention. A computerized urn randomization procedure will be used to randomize participants and balance groups on three baseline characteristics that may independently influence the main outcome measures of ART adherence and viral load. Specifically, depression, active drug use, and low health literacy have all been shown to be associated with reductions in ART adherence. Thus, we will use presence of current depression (Y/N); self-reported recent Cocaine or Opiate use (Y/N); and TOFHLA (a health literacy measure; see Assessments) score  $\leq$  the rolling median (Y/N) as the stratification variables in the present study. While it might be desirable to stratify on additional variables, increasing the number of variables is not practical given the study's sample size.

**Procedure.** After obtaining informed consent, the student investigator will complete the intake interview. First, the ASI-Lite will be administered to finish determining eligibility. If the participant is eligible for the study, the TOFHLA will be administered. While the participant is completing the ASI-Lite and the TOFHLA, the student investigator will call the Outreach Coordinator to obtain depression status, CD4 count, HIV-1 RNA levels, and drugs of abuse history information. Once the participant has completed the TOFHLA and information regarding recent drug use and depression status, group assignment can be determined. The student investigator will then call the principal investigator,

[name], and give the answers to the stratification variables. The principal investigator will then run the urn randomization procedure and relay the group assignment to the student investigator. The participant will then complete the rest of the surveys (Visual Analog Scale for self-reporting ART adherence, MOS-HIV, Patient Reactions Assessment, SteadyRx Reminder Enrollment Form, and Contact Information Sheet).

**Notifying Outreach Coordinator.** After the participant has been randomized and is completing the rest of the assessments (see above), the student investigator will inform the Outreach Coordinator of the group assignment. The Outreach Coordinator will bring the necessary materials to complete the intake to the participant (MEMS cap, CT Payer card, and smartphone (if in SteadyRx group). After the Outreach Coordinator is notified of study condition, and the assessments are finished, the student investigator will inform the participant of study condition.

**Notifying Participant of Study Condition.** The student investigator will notify the participant of the result of the randomization procedure.

If the result is the SteadyRx group, the student investigator will say the following:

“You have been assigned to the SteadyRx group. This means that you are able to be paid \$30 each month for coming here and completing an interview with our outreach staff. This also means that you will be provided with a cell phone for 6 months. You will be provided with a medicine cap that will go on top of your prescription HIV medication bottle. You are responsible for keeping track of both of these items. If either of these items are lost, stolen, or sold, you will be penalized. If you keep your cell phone for the whole study, you will receive \$100 at the end of the study. Instead of receiving \$100 for returning the cellphone, you may choose to keep it. Each time you bring your medicine cap back to an interview, you will receive \$20. On the cell phone, you will find an app called SteadyRx, which we will teach you how to use now. Do you have any questions?”

If the result is the control group, then the student investigator will say the following:

“You have been assigned to the control group. This means that you are able to be paid \$30 each month for coming here and completing an interview with our outreach staff. Each month, we’ll set up an appointment for the following month and our outreach staff will be calling you from time to time to remind you about your appointments and the money you can make. You will be provided with a medicine cap that will go on top of your prescription HIV medication. Each time you bring the medicine cap to an assessment interview, we will pay you \$20. We will make an appointment with you for our next meeting today before you leave. I’d also like to provide you with \$50 for coming here today, and you may also have two bus tokens if you’d like. Do you have any questions?”

If the participant was found ineligible for the study due to answers given in the ASI-Lite, then the student investigator will read the following script:

“Unfortunately, you did not qualify for the study. The good news is that we are paying you \$50 for your time today. [name] should be down any moment with the card. We want to emphasize that we thank you for coming out and taking time to complete these assessments. This also is a very important part of our study. We also wanted to note that this will not change your care at the CCP or at Johns Hopkins. Thank you again for your time.”

**MEMS Cap.** All participants will receive a MEMS cap which is to be placed on the cap of their prescription HIV medication. The intake assessment cannot take place if the participant did not bring their pill bottle. The student investigator is responsible for initiating a participant into the MEMS database located at <http://www.mwvaardex.com/>. The student investigator should use their own personal login information to access the database.

**Assigning Materials.** All participants will be assigned a CTPayer card which will be loaded with \$50 for completing the intake assessment, regardless of study group assignment. All participants will sign a SteadyRx Material Acknowledgement Form that specifies what materials they received. A log will also be updated with this information.

**CT Payer.** All debit cards will be issued and loaded through CTPayer. The outreach coordinator will be responsible for issuing the debit card. Prior to giving the debit card to the participant, the outreach coordinator will call the student investigator in Kalamazoo and inform them of the specific card being issued to the participant. The principal investigator and student investigators will be responsible for assigning the debit card to participants and paying participants through the CTPayer system. Immediately after being informed of the debit card information, the student investigator will login to the CTPayer system with the lab account through their website <https://partners.payoneer.com/> and change the Payee ID of the specific debit card to the participant's assigned participant ID.

**SteadyRx Group Only.** Participants in the SteadyRx group will receive a Smartphone with the SteadyRx application downloaded onto it. Participants will be required to complete PillWatch protocol.

**Creating Participant SteadyRx accounts.** The responsibility of creating Motiv8 Systems accounts for participants in the SteadyRx group will be the student investigators' in Kalamazoo. In order to access the backend of the SteadyRx, the student investigators will create an admin account for themselves using the credentials given by the principal investigator. The student investigators will then navigate to the following URL: <http://steadyrx.red5hift.com>.

The Clients tab should be the default start page. Click “Add Client” in order to begin the process. Both their login and their alternate ID will be the participants’ PTID. The password will be selected from the list of passwords created by the principal investigator on the shared Google Drive. Once a password has been assigned to a participant, cross that password out on the list. After creating the account, the student investigator must then assign participant to either the OnePerDay or TwoPerDay program. This will correspond to whether the participant must take their antiretroviral medication once or twice per day. The student investigator will create either one or two dose windows accordingly entering the participants’ cellphone number followed by “@myboostmobile.com” where it asks for an email address. Finally, the student investigator will add the participants’ healthcare contacts to the InTouch contacts.

**Preparation for the First 30-Day Assessment and Participant Departure.** After the participant has been informed of their study condition, outreach staff should then set up the first 30-day assessment appointment, provide the participant with an appointment card, confirm their contact information and release the participant. The student investigator should make a \$50 payment to the participant, update the Materials Assignment records, and set up a new data sheet.

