## Assessments

An intake assessment (e.g., ASI-Lite) will be collected prior to randomization. Additional assessments will be conducted at 30-day intervals throughout the 6-month intervention period. All assessment forms are listed in the [List of Manual Forms](#). Complete descriptions of each assessment and the schedule of delivery for each assessment is provided below.

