**Inclusion/Exclusion Criteria:**

Applicants will be eligible to participate in the study if they:

- a) Are 18 to 100 years old
- b) Are HIV positive
- c) Have a primary care physician who is providing their HIV-related care including prescribed ART
- d) Meet criteria for substance use disorder
- e) Speak fluent English
- f) Can operate a smartphone

Applicants will be excluded if they:

- a) Report current suicidal ideation. **Immediately initiate suicide prevention protocol in accordance with CCP policy/practices.**
- b) Report auditory or visual hallucinations. **Immediately alert study doctor if a participant has active hallucinations.**
- c) Are currently participating in any other HIV/AIDS related or medication adherence related research studies.

**Informing Participants of Eligibility/Ineligibility.** The applicants should never be told why they are eligible or ineligible. This policy will prevent the community from learning about the eligibility criteria. This is imperative, since knowledge of the study criteria could result in applicants either falsely self-reporting characteristics in an effort to get admitted to the study. All staff members should be intimately familiar with the policies related to eligibility described in this treatment manual.

**The Intake Interview.** The interview will be conducted by using the [SteadyRx Intake Assessment Checklist – Outreach Coordinator](#) and the [Intake Assessment Checklist – WMU Staff](#). This interview includes the Smartphone Assessment Protocol, the Testing of Functional Health Literacy in Adults (TOFHLA), the Beck Depression Inventory (BDI-II), the Visual Analog Scale for self-reporting ART adherence, the Medical Outcomes Study HIV Health Survey, Addiction Severity Index – Lite (ASI- Lite), and the Patient Reactions Assessment.

The [Smartphone Assessment Protocol](#) assesses whether participants can operate a smartphone.

The [Test of Functional Health Literacy in Adults](#) (TOFHLA) – a standard measure of health literacy which has been shown to predict ART adherence.

The [Visual Analog Scale for self-reporting ART adherence](#) which has been recommended as providing the highest quality self-reports of ART adherence in several recent studies.

The [Medical Outcomes Study HIV Health Survey](#) is a widely used assessment of quality of life for HIV/AIDS patients that assesses perceived physical and mental health.

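### Minor, exploratory only: the urn is run before the intake MOS-HIV, VAS and Patient Reactions Assessment, so the MOS-HIV baseline is taken after allocation, though before the participant is told the arm

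*Combined protocol and SAP*

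**What the plan says.** The Procedure paragraph under Random Assignment to Study Conditions gives the order of the intake visit. The ASI-Lite comes first and then the TOFHLA, while depression status and drug use history are obtained by telephone. The principal investigator then runs the urn and will "relay the group assignment to the student investigator". After that step comes "The participant will then complete the rest of the surveys (Visual Analog Scale for self-reporting ART adherence, MOS-HIV, Patient Reactions Assessment", followed in the same list by "SteadyRx Reminder Enrollment Form, and Contact Information Sheet".

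The next paragraph, Notifying Outreach Coordinator, has the coordinator told the arm at this stage: "After the participant has been randomized and is completing the rest of the assessments". The coordinator then brings the MEMS cap and payment card, plus a smartphone for SteadyRx participants only. The participant hears the arm last: once the coordinator has been notified "and the assessments are finished, the student investigator will inform the participant of study condition".

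The Intake Interview paragraph lists "the Visual Analog Scale for self-reporting ART adherence, the Medical Outcomes Study HIV Health Survey" and the Patient Reactions Assessment among the intake instruments. The Secondary and Exploratory Analyses section states that the CD4, viral load and MOS-HIV models control for baseline. MOS-HIV is classed as exploratory under Secondary Outcome Variables.

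**The concern.** A baseline covariate earns its place in a randomized comparison because allocation cannot have influenced it. A self-reported score collected after allocation, with staff aware of the arm, loses that guarantee. If it differs between arms because of the allocation, adjusting for it moves the estimated treatment effect.

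Two routes are plausible:

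- **Staff.** The student investigator knows the arm while the surveys are completed, and the university team controls the assessment computer remotely (Procedures for Initiating the Intake Assessment).
- **The smartphone.** The coordinator is told the arm during the surveys and brings a phone for one arm only. Nothing says to hold it back until the surveys end.

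The order also creates a procedural conflict. Under Inclusion/Exclusion Criteria and Checklist, a person who permanently stops the interview before it is complete counts as dismissed. Under the Analytic plan, everyone randomized is included. A participant who stops after the urn but before MOS-HIV falls under both rules.

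**Working it through.** The plan states no power, SD or effect size for MOS-HIV, so there is no figure to reproduce. The check has two parts.

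**1. Which analyses use the three scales**

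| Item | Used as a baseline covariate? |
|---|---|
| MOS-HIV | Yes (Secondary and Exploratory Analyses) |
| VAS, Patient Reactions Assessment | None named |
| Primary MEMS and viral load models | Do not use these scales |
| Stratification variables (depression, drug use, TOFHLA) | Collected before the urn |
| CD4 and viral load baselines | Laboratory values obtained before the urn |

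So one exploratory model is affected. Separately, the Analytic plan lists quality of life among the baseline factors to be described, and the section on data analysis for future publication compares groups on intake variables. Scores taken after allocation could therefore be presented as baseline.

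**2. What adjustment would do**

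Assumptions: SD of 1 at every time point, correlation r between any two time points, no true effect. Let d be the arm difference in baseline score caused by the allocation, and f the arm difference in follow-up score caused by arm knowledge alone. The within-arm slope is r, so:

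- bias of the adjusted estimate = f - r x d
- bias of the unadjusted estimate = f

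The baseline shift therefore contributes -(r x d). With assumed r of 0.5 and 0.7:

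| Assumed d | Contribution, r = 0.5 | Contribution, r = 0.7 |
|---|---|---|
| 0 | 0 | 0 |
| 0.1 SD | -0.05 SD | -0.07 SD |
| 0.2 SD | -0.10 SD | -0.14 SD |

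This equals the total bias only if f = 0. If follow-up shifts equally, f = d = 0.2, the adjusted bias is 0.2 - 0.5 x 0.2 = 0.10 SD, or 0.2 - 0.7 x 0.2 = 0.06 SD, against 0.20 SD unadjusted. The net bias can thus have either sign.

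**Precision.** The total is 50 participants (Design), about 25 per arm. With m complete follow-ups:

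- SE adjusted = sqrt((2/25) x ((1 + (m-1)r)/m - r^2))
- SE unadjusted = sqrt((2/25) x (1 + (m-1)r)/m)

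| m | r | SE adjusted | SE unadjusted | Ratio |
|---|---|---|---|---|
| 1 | 0.5 | 0.2449 | 0.2828 | 1.15 |
| 1 | 0.7 | 0.2020 | 0.2828 | 1.40 |
| 6 | 0.5 | 0.1633 | 0.2160 | 1.32 |
| 6 | 0.7 | 0.1442 | 0.2449 | 1.70 |

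Even at d = 0.2 SD, the contribution of 0.10 to 0.14 SD is below the adjusted SE for the same r, for both m = 1 and m = 6.

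**The case against.** The strongest reply is that the main safeguard is already in place: the participant does not know the arm when answering. The text also leans toward self-completion. The coordinator "brings the participant to the computer terminal", Data Management refers to computer-assisted self-interviews, and the instruction to read questions aloud belongs to the monthly visits. Remote control of a terminal is not evidence of influence on a quality-of-life score, and the documents do not say when the smartphone is brought or shown. All of this stands. It makes the shift uncertain and probably small, but it does not restore a pre-allocation baseline.

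Four stronger readings are tempting and are not supported.

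- **That the plan contradicts itself on timing.** The Assessments section says "An intake assessment (e.g., ASI-Lite) will be collected prior to randomization". The instrument it gives as an example does precede the urn, and the sentence does not claim that every intake instrument does.
- **That the reminder enrollment form reveals the arm.** It is listed after the three scales and carries no arm restriction, unlike the smartphone.
- **That type I error is inflated by a known amount.** With f = 0, d = 0.2 SD and six follow-ups, the normal approximation gives 9.4% to 16.3%. That case supposes a shift before the arm is disclosed and none afterwards, although monthly MOS-HIV is read aloud to participants who know their arm. The figures are conditional illustrations only.
- **That the published MOS-HIV result is biased.** The section on data analysis for future publication names only the stratification variables as GEE covariates. Whether the baseline adjustment was kept is unclear; if it was not, the bias formula does not apply.

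That section is also written in the past tense, so reordering cannot help participants already enrolled. That too stands.

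**Conclusion.** The point holds as a minor design weakness confined to an exploratory measure. The MOS-HIV baseline used for adjustment is taken after allocation and after staff know the arm, but before the participant is told. Bias is possible and not shown; with no shift there is none.

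A baseline shift of d would contribute -(correlation x d): 0.05 to 0.07 SD in magnitude for an assumed 0.1 SD shift, and 0.10 to 0.14 SD for 0.2 SD, with correlations of 0.5 to 0.7. The documents supply neither the shift nor the correlation. Because follow-up reporting is also open to arm knowledge, neither the net bias nor the type I error can be derived from them. The primary MEMS and viral load analyses are not affected. Confidence is medium, since the consequence depends on how the surveys are delivered at intake and on which MOS-HIV model is reported.

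**What to change.** **For the procedure.** Move the call to the principal investigator and the urn run to after the VAS, MOS-HIV and Patient Reactions Assessment. Coordinator notification, materials, the reminder form, app training and the arm script then follow. Nothing the urn needs comes from the moved surveys. The change also avoids randomizing someone who stops before completing these scales. It stays within the same visit of about two hours and needs no new staff or forms; the only downside is a short wait for the assignment at the end. It protects the baseline only and leaves monthly MOS-HIV unblinded.

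**For data already collected.**

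1. Disclose that the three scales were taken after allocation but before disclosure to the participant, and label them so wherever they appear in the intake comparison.
2. State whether the reported MOS-HIV model includes the baseline value, since the two analysis sections differ on this.
3. If it does, add the unadjusted model as a sensitivity analysis. It removes the baseline contribution but not any follow-up shift, and its SE is about 1.2 to 1.7 times larger under the assumptions above.

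The cost is a sentence or two of reporting and at most one extra exploratory model.

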### Design

This randomized controlled pilot study features a parallel group design. Participants (N = 50) will be randomly assigned to one of the two groups: Treatment as usual (TAU) or the SteadyRx-supported antiretroviral adherence group (SteadyRx). We will randomize using urn stratification to promote equal numbers of individuals in each group and balanced distributions within a dichotomized covariate expected to be associated with the outcome. Stratification variables are current depression (Y/N); self-report of problem drug use in the last 30 days (Y/N); and TOFHLA score  $\leq$  the rolling median (Y/N). Study participation will last for six months from the date of randomization.

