**Elements of the monthly assessments.** The outreach coordinator will be responsible for:

- Attaching the MEMS reader to the assessment computer
- Obtaining CD4 and HIV-1 RNA levels from medical record
- Scheduling the next monthly assessment

**Reading a participant's MEMS cap.** Upon a participant's arrival, the outreach coordinator will place the MEMS cap on the reader and initiate the reading.

Tutorials for reading a MEMS cap will be made available to the outreach coordinator from the student investigators as well as from the help section located within the database. They will obtain CD4 and HIV-1 RNA levels from the medical record or from printed labs given by the participants. The outreach coordinator will inform WMU staff of the participant's arrival and any new lab information.

**Conducting Monthly Assessments.** The remainder of the monthly assessment will take place over the phone with one of the student investigators located in Kalamazoo. The student investigator is responsible for reading each assessment question aloud to the participant and filling in the answers accordingly. Upon the completion of both the MEMS reading and phone assessments, the participant should be paid \$50. If the participant brought in recent CD4 and RNA lab readings and have an undetectable viral load, they should be paid \$100, up to twice during the study. All relevant data logs should be updated (see [Monthly Assessment Checklist – WMU Staff](#)).

The student investigator is solely responsible for conducting the following assessments:

- [Visual Analog Scale for self-reporting ART adherence](#)
- [Medical Outcomes Study HIV Health Survey](#)
- [Addiction Severity Index-Lite](#)
- [Patient Reactions Assessment](#)

In addition to the previous assessments, student investigators are also responsible for conducting the following assessments for participants in the SteadyRx group:

- [SteadyRx Satisfaction Questionnaire](#)
- [Software Usability Measurement Inventory](#)

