## MAIN STUDY DISCHARGE

Main Study Discharge will occur for all participants irrespective of group assignment upon completion of the 6th Main Study Assessment and should be scheduled for study day 180. Outreach staff are responsible for Main Study Discharge and should follow the [Discharge Checklist](#). The Main Study Discharge interview is identical to the monthly assessment interview aside from collecting the participant's smartphone and MEMS cap. The participant is entitled to a \$100 incentive for keeping the same smartphone for the entire study period and returning it during this interview. Alternatively, they can forego the \$100 and keep the smartphone. They will be told of this choice during the intake interview and reminded at study discharge. If they choose to keep the phone, immediately remove payment and contact information from the Boost Mobile account. Also change the pin to their participant ID and make a note in the phone number records log.

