### **Analytic plan for SteadyRx study**

Descriptive statistics (means and standard deviations or proportions) will be calculated for demographics, baseline participant factors (e.g., quality of life, substance use), treatment history, health literacy, and application ratings and engagement. All analyses will be intent to treat; all participants who are randomized will be included. All analyses will be adjusted for the pre-specified covariates used for stratification. All hypothesis tests will be two-sided,  $\alpha$  will be set at 0.05, and p-values for secondary analyses will be corrected to maintain  $\alpha=0.05$ . Based on our past research and the automated collection of our primary outcome measure, we expect relatively little missing data and little difference in the rates of missing data across groups. We plan to conduct analyses in which missing samples are assumed to represent the adverse outcome (e.g., missing = drug positive) and in which missing data will be ignored (missing = missing). The “missing positive” method is more conservative and will be considered the primary method.

Primary Outcomes. The effects of the intervention relative to the control group on the dichotomous monthly adherence measure will be analyzed with a longitudinal logistic regression model with treatment group and time as covariates. The group term, representing the between-group difference averaged over time, will be the primary coefficient of interest. Correlation among outcomes over time within individuals will be handled using the method of Generalized Estimating Equations (GEE). The dichotomous viral load variable (<400 HIV-RNA/mL, y/n) will be modeled with an analogous model but with only two follow-up measures.

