### **Data Analysis to be reported in future publication**

Groups were compared on intake variables using Fisher’s exact tests for dichotomous variables, chi-square tests for categorical variables with more than two categories, and t-tests for continuous variables. Outcome measures were analyzed using generalized estimating equations (GEE) (Zeger, Liang, & Albert, 1988), including and excluding the stratification variables as covariates. GEE results presented use the covariate model unless otherwise specified. Planned comparison t-tests were used to compare between and within groups on outcome measures at time points 1 and 6. Analyses were intent-to-treat and conducted using SAS version 9.3. Missing data were treated as missing-missing. Analyses were two-tailed with statistical significance set at alpha of .05. Due to the error in the collection of biometric data, analyses for these variables are not included.

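### The scripts warn only SteadyRx participants about losing the MEMS cap, and the primary missing-data rule, labelled conservative, would turn any resulting excess of missing control months into apparent benefit

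*Combined protocol and SAP*

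**What the plan says.** Both arms receive a MEMS cap, and primary outcome 1 (monthly yes/no, 95% of doses on time) is read from it.

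- **SteadyRx script** (Procedures, Notifying Participant of Study Condition): the participant must keep track of phone and cap, and "If either of these items are lost, stolen, or sold, you will be penalized". The penalty is not defined anywhere in the documents.
- **Control script** (same section): "You will be provided with a medicine cap that will go on top of your prescription HIV medication", then the payment for bringing it. It mentions neither responsibility nor loss.
- **Equal in both scripts**: $30 per interview and $20 for bringing the cap. Under Monthly Assessments, reminder calls and no-show follow-up are also the same.
- **SteadyRx only**: a study phone, and at discharge a $100 "incentive for keeping the same smartphone for the entire study period and returning it during this interview", with keeping the phone as the alternative. That discharge interview, on day 180, is also the sixth outcome assessment.
- **Reading the cap** (Monthly Assessments): "Upon a participant's arrival, the outreach coordinator will place the MEMS cap on the reader and initiate the reading".
- **Analytic plan**: little missing data, and little difference between arms, is expected from past research and automated collection. Missing is scored as the adverse outcome in one analysis and left missing in another. Of the first, the plan says this "method is more conservative and will be considered the primary method".
- **Data Analysis to be reported in future publication**: missing data were left as missing. Scoring them as failures is not mentioned.

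**The concern.** Bottle openings are recorded automatically, but they reach the database only if the participant still has the cap and brings it in. The scripts give the two arms different reasons to keep it. The phone and the day-180 choice may also make SteadyRx participants easier to reach and more likely to return.

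If controls lose more months as a result, scoring those months as non-adherent lowers the control rate more than the SteadyRx rate. Part of the difference on primary outcome 1 would then reflect return of the cap, not taking of ART. The conservative label would hide this, because it implies that the rule can only work against the intervention. The two analysis sections also leave it unclear which rule governs the main result.

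**Working it through.** The plan gives no adherence rate, missingness rate, effect size or power, so there is no figure to reproduce. The check tests the mechanism under stated assumptions.

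**Inputs from the documents.** "Participants (N = 50) will be randomly assigned to one of the two groups", with an urn scheme to "promote equal numbers of individuals in each group", taken here as 25 per arm; six monthly assessments; a GEE logistic model with the time-averaged group term as primary; "Analyses were two-tailed with statistical significance set at alpha of .05".

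**Assumed.** No true effect; true monthly adherence p of 0.3 to 0.7 in both arms; SteadyRx missing 5%; control missing 5% to 35%.

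**Step 1: one month, missing scored as failure.** Let m be the missing fraction and q the true adherence among missing months. The apparent rate is p − m × q. If missingness is unrelated to adherence, q = p, and the false gap is p × (m control − m SteadyRx).

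- 5% v 20%, p = 0.5: 0.5 × 0.95 = 0.475 v 0.5 × 0.80 = 0.400. Gap 7.5 points, OR (0.475/0.525)/(0.400/0.600) = 1.36.
- 5% v 20%, p = 0.7: 0.665 v 0.560. Gap 10.5 points, OR 1.56.
- 5% v 25%: gaps of 6, 10 and 14 points at p = 0.3, 0.5 and 0.7.
- 25% v 5% (SteadyRx loses more): −6, −10 and −14 points.
- q = 0 (every missing month truly non-adherent): no bias.

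**Step 2: six months.** Simulated GEE with group and time, independence working correlation, robust standard errors, no stratification covariates, random-intercept SD 2 and 1,500 replicates per setting. Two-sided rejection with no true effect, 5% v 25% missing (median OR in brackets):

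| True adherence | Missing in every month | Cumulative dropout by month 6 | Day 180 only |
|---|---|---|---|
| 30% | 12.4% (1.40) | 6.5% (1.24) | 5.1% (1.03) |
| 50% | 17.3% (1.50) | 7.9% (1.24) | 4.5% (1.06) |
| 70% | 36.5% (1.81) | 12.0% (1.43) | 6.5% (1.12) |

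With equal 5% missingness, rejection is 4.1% to 5.5%. The day-180 column stays near nominal because one visit in six carries the gap: at p = 0.5 the average shift is 0.5 × 0.20 / 6 = 1.7 points.

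**Step 3: missing left as missing.** In the same simulations the median OR is 0.97 to 1.04 and rejection is 3.8% to 6.0% in every setting, including 5% v 35%. This holds because the simulated missingness is unrelated to adherence. In general the observed rate is (p − m × q)/(1 − m). At p = 0.5, q = 0 and 5% v 20% missing, it is 0.5/0.95 = 52.6% v 0.5/0.80 = 62.5%, a false gap of 9.9 points against SteadyRx. Neither rule is safe in general.

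**The case against.** Several points against the concern stand.

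- **Unequal retention is not shown.** A reader might infer from the scripts that controls will lose more data. The documents do not support that: attendance and cap payments, reminder calls, no-show contact and possible home visits are the same in both arms, and losing the cap already costs either arm $20 per visit.
- **The $100 is weak evidence on its own.** It is for the phone, not the cap, at one visit of six, and a participant may keep the phone instead. It matters only if it holds people in the study over several months or brings back a cap containing earlier data.
- **A missed visit need not be a missing month.** The cap records when the bottle is opened, so a later reading may recover the gap. The plan does not say that recoverable months count as missing, which makes a constant large gap less plausible.
- **The direction is uncertain.** An undefined penalty could also keep away a SteadyRx participant who has lost an item.
- **The scripts may not be the whole story.** All participants sign a materials form whose text is not in the documents. It may contain a loss term for controls, though it would not remove the difference in the spoken scripts.
- **The analysis for publication uses the other rule.** A reader might infer that the reported result rests on missing scored as failure. That section says otherwise. This route to a false effect then disappears if missingness is unrelated to adherence, but the conflict with the analytic plan remains.

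**Conclusion.** The point holds as a conditional risk. The arms are told different things about the device that measures primary outcome 1, and the plan's primary rule has no built-in direction between arms. Its bias follows whichever arm loses more data. With 5% v 20% missing in every month and equal true adherence, the false benefit is 7.5 points at 50% adherence and 10.5 at 70%. It is smaller under dropout and near nil if only day 180 is affected. These sizes rest on assumed rates and on missingness unrelated to adherence.

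The documents do not show that retention differs, or that a treatment effect would be an artefact. The firmest defects are textual: the unequal cap wording, the unsupported conservative label, and two analysis sections that name different missing-data rules. The point is of moderate importance, held with moderate confidence.

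**What to change.** 1. If enrolment is still open, use the same cap-responsibility and loss wording in both assignment scripts. The publication section is in the past tense, so this may come too late.
2. Fill a month with a missed visit from the next date-stamped cap download, and treat only unrecovered months as missing.
3. State one primary missing-data rule, the same in the analytic plan and the publication section. Remove the claim that scoring missing as adverse is conservative. Report missing months by arm and by month. The plan already has both missing-data analyses; add a sensitivity analysis that varies the assumption separately by arm, for example q in the formula above.

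Optional: offer controls a matching day-180 payment for returning the cap, at most 25 × $100 = $2,500 if there are 25 controls. Detaching the phone payment from that visit is not clearly free, because the phone is collected there. The study phone delivers the intervention and cannot be matched simply, so reporting missingness by arm matters whatever else is changed.

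Items 1 to 3 cost minor script and analysis work. Items 2 and 3 can still be done after enrolment closes.
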